4.4.3 Exploratory Endpoints

Exploratory endpoints will be driven by a fundamental analysis of mean changes in clinician rating scales and patient QoL and PRO instruments compared from baseline to one or more visit timepoints. Mean changes in epigenetic markers also will be assessed. In addition, data captured by the health tracking wearable device will be assessed. For all exploratory endpoints, appropriate statistical methods will be employed as described, more generally in Section 13.5. A formal outline of the statistical methods to be employed will be detailed in the SAP.

- At Screening, participants will confirm that they have had a traumatic event, captured in the LEC-5 and that they have a minimum score of at least 33 as determined the PCL-5, respectively.
- Mean changes from baseline to various study visit timepoints (e.g., Study Day 7) will be calculated for the following instruments:
 - General Anxiety Disorder 7 Item Scale (GAD-7)
 - Patient Health Questionnaire-9 (PHQ -9)
 - Healing Experience of All Life Stressors (NIH HEALS)
 - Brief Pain Inventory (BPI)
 - Columbia-Suicide Severity Rating Scale (C-SSRS)

CONFIDENTIAL

- Profile of Mood States (POMS)
- Sheehan Disability Scale (SDS)
- Watts Connectedness Scale (WCS)
- Mystical Experience Questionnaire-revised (MEQ30)
- Challenging Experience Questionnaire (CEQ)
- 5-Dimensional Altered States of Consciousness Rating Scale (5D-ASC)
- Alcohol Use Disorders Identification Test (AUDIT)
- Drug Use Disorders Identification Test (DUDIT)
- Mean changes in epigenetic markers from baseline to various timepoints will be calculated for psychiatric and cardiovascular genes.
- Data collected by a health tracking wearable device such as nightly sleep duration, sleep latency, sleep efficiency, heart rate and heart rate variability during sleep, and daily steps will be calculated.

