7.1.2 Pre-screening

Prospective participants may be interviewed by telephone to determine whether they might be suitable candidates to participate in the trial. At the start of the telephone interview, interviewees will provide verbal consent confirming that they are willing to share personally identifiable information and their personal health information to determine if they are likely to qualify for participation in the trial.

The pre-screening interview will include questions about the participant's medical and psychiatric history, current treatment, etc. The interviewees will be asked to provide responses to the 17-question Life Events Checklist for DSM-5 (LEC-5) and the 20-question PTSD Checklist for DSM-5 (PCL-5). Qualified study site staff will provide individuals that pass the pre-screening assessment with IRB-approved study information and consent materials for review and consideration.

- If the prospective participant is not eligible or not interested in taking part in the trial their personal information will be destroyed at, apart from the summary reason for ineligibility, which will be retained on the Screening Log. An eCRF will not be completed for candidates who are not enrolled.

Pre-screening information will be retained for candidates who provide specific permission via verbal consent for utilization and retention of this information and who and provide written informed consent to participate in the trial. The Screening Log will be completed to include the qualified participant's screening number. The Screening Log will be maintained and kept up-to-date and be available for review by the study site monitor.

Table 1

Schedule of Events

Activity	Pre-Screen	Screening Period		Day 1	Day 2	Day 4 (Virtual)	Day 8 (±1 day)	EoT Day 30 1 Month (±5 days)	LTFU 3 Month (±7 days)
		-30 - to -1 (Can be extended)							
			Prior to Study Day 1						
Pre-Screen Verbal Consent ¹	X								
LEC-5 [^]		X							
PCL-5 [^]		X							
Informed Consent		X							
Medical History	X	X		X	X	X	X	X	X
Concomitant Medications	X	X		X					
Eligibility Criteria	X	X		X					
Height / Weight ²		X					X	◆ ¹⁴	
Physical Exam ³		X					X	◆ ¹⁴	
Vital Signs ⁴		X		X	X		X	X	X
Urine Pregnancy Test ⁵		X							
Urine Drug / Alcohol Tests		X		X				X	X
Clinical Laboratory Tests ⁶		X ⁶		X			X	X	
Electrocardiogram ⁷		X		X			X		
Dispense/Collect Wearable		X						◆ ¹⁴	X
Saliva – Epigenetic Test				X			X	◆ ¹⁴	
Pharmacokinetic Test ⁸				X					
Administer Study Drug				X					

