9. GAD-7: If a participant's score is ≥15 at Screening or on Study Day 1 (prior to study drug administration), the participant is not eligible for treatment.
10. PHQ-9: If a participant's score is ≥20 at Screening or on Study Day 1 (prior to study drug administration), the participant is not eligible for treatment.
11. C-SSRS: If at Screening or on Study Day 1 a participant's 'suicidal' assessment is scored as Category 4 (i.e., Active Suicidal Ideation with Some Intent to Act, without Specific Plan) or Category 5 (Active Suicidal Ideation with Specific Plan and Intent), the participant is not eligible to continue to participate in the trial and should be referred for appropriate psychiatric care.
12. POMS: On Study Day 1, after all protocol-mandated activities are complete, the clinician will assess the result of the POMS. If the posttreatment POMS score is not ≤125% of the baseline, pre-dose, value, the patient should be held overnight for observation. [Otherwise, if the score is ≤125% of the baseline, and if there are no other problems, the patient may be discharged to home (accompanied by a trusted adult).
13. AUDIT / DUDIT: The AUDIT and DUDIT should be completed at the Study Day 30 / End-of-Treatment visit if a participant prematurely discontinues from the trial (for any reason) and will not undergo the 3-month, Long-Term Follow-up visit.
14. ◆: The diamond reflects tests, examinations, assessments or other procedures that are to be completed the EoT visit if a participant is prematurely discontinued from further involvement in the trial and the particular protocol-mandated activity was not performed at the Study Day 8 visit.
15. **The One-to-One session as well as the Group session require participants to return to the study site on separate days. [Thus, the Screening Period can require three (3) visits to the study site.]**

Table 2
Study Day 1 Schedule of Events

Activity	Pre-Dose	Dose		Post Dose							
		Time 0	30 mins	60 mins	90 mins	120 mins	150 mins	180 mins	240 mins 4 hours	4.5, 5.0, 5.5, 6.0, 6.5, 7.0 and 7.5 hours	480 mins 8 hours
Medical History	X										
Concomitant Medications	X										
Eligibility Criteria	X										
Height / Weight ²	X										
Vital Signs ⁴	X	X	X	X	X	X	X	X	X	X*	X
Urine Pregnancy Test ⁵	X										
Urine Drug / Alcohol Tests	X										
Clinical Laboratory Tests ⁶	X										
Electrocardiogram ⁷	X										
Saliva – Epigenetic Test	X										
Pharmacokinetic Test ⁸	X	X	X	X	X	X	X	X	X		X

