7.1.3 Screening Period (Day -30 to -1)

If after the pre-screening telephone interview, the study site staff and/or the investigator feel the candidate may be suitable for the study, a Screening visit will be scheduled.

The initial Screening Visit will include the following protocol mandated activities, tests, examinations, assessments and procedures:

- Explain and obtain written informed consent from the candidate prior to performing any study-specific tests or evaluations.
- Issue a 3-digit screening number and record the appropriate information on the Screening Log.
- Review the participant's medical and psychological history including current and past medications and therapies.
 - Have the participant sign a medical release form to allow the Investigator to review his/her medical records to ensure the participant has no underlying medical conditions that would preclude their participation in the trial and confirm the PTSD diagnosis.
- Review the LEC and PCL-5 checklists.
- Review with female participants of childbearing potential their ability to become pregnant and commitment to practice appropriate birth control as defined in this protocol for the total duration of the study.
- The following clinician rating scales and participant QoL and PRO instruments should be administered and/or completed by the participant, respectively:
 - LEC-5 (at least one traumatic event causative for a diagnosis of PTSD)
 - PCL-5 (a score of at least 33)
 - GAD-7 (scores of ≥ 15 will exclude the participant)
 - PHQ-9 (scores of ≥ 20 will exclude the participant)
 - NIH HEALS
 - BPI
 - C-SSRS (category ratings of 4 or 5 will exclude the participant)
 - SDS
 - AUDIT
 - DUDIT
- Collect vital signs (blood pressure, pulse, body temperature, respiratory rate and pulse oximetry).
 - Perform a medical history directed physical examination. The examination will involve the following procedures:
 - Height/weight.
 - Examination of head, eyes, ears, nose, throat, skin, heart, lungs, abdomen and extremities.

CONFIDENTIAL

- Brief neurological exam (cranial nerves 2-12, sensory, motor, reflexes and cerebellar function).
- Obtain 12 lead ECG
- Collect urine for the following laboratory analyses:
 - Urine pregnancy test in women of childbearing potential.
 - Qualitative rapid urine drug screen.
 - Qualitative urine ethyl glucuronide (EtG) test to assess alcohol consumption.
- Collect a blood sample for clinical laboratory evaluations.

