If the participant prematurely discontinues from the trial, this will be their last study visit, unless there is an ongoing adverse event that will continue to be monitored until resolution or until the Investigator and Medical Monitor determine that no additional follow-up is medically necessary.

Otherwise, the participant will return to the study site for the final 3-month, LTFU, visit.

7.1.9 3-Month Long-Term Follow-up (LTFU) Visit

Approximately three months (i.e., 90 days) after Study Day 1, participants will return for the final, 3-month, Long-Term Follow-up (LTFU) visit. At this visit, a number of protocol-mandated tests, examinations, assessments and procedures will be done as described below.

- Inquire about any changes in the participant's health in a non-suggestive manner; however, any changes noted will not be considered adverse events unless they either were noted prior to the Study Day 30 / EoT visit and/or are considered to be 'possibly' or 'probably' related to study drug administration.
- Review concomitant medications/therapies (including psychotherapy and healthcare utilization).
- Perform a brief physical exam and obtain weight (only if Study Day 8 visit was not completed).

CONFIDENTIAL

- Obtain vital sign measurements.
- Obtain urine samples for:
 - Qualitative rapid urine drug screen.
 - Qualitative urine ethyl glucuronide (EtG) test to assess alcohol consumption.
- Review participant's use of health tracking wearable device and collect the device and download the data to the trial database.
- Administer and/or have the participant complete the following clinician rating scales and participant QoL and PRO instruments, respectively:
 - GAD-7
 - PHQ-9
 - BPI
 - NIH HEALS
 - C-SSRS
 - AUDIT
 - DUDIT

Upon completion of the 3-month, long-term follow-up visit and after the study site staff obtain all outstanding data, participants will have completed the study, except if there is an ongoing adverse event that the Investigator and/or Medical Monitor believe warrants continued monitoring until resolution or until it is determined that no additional follow-up is medically necessary.

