12.5. Analyses of Exploratory Objectives

The following is an outline of the planned analyses to be done for various exploratory objectives (and associate endpoints).

- Analyses of changes from baseline for continuous questionnaires will be summarized descriptively by visit. and analyzed using repeated measures ANCOVA or generalized linear mixed modeling, as described in the SAP. The statistical significance of the change from baseline ($p < 0.05$) will be determined for each measure. 95% confidence intervals will also be derived.
- Change in average sleep duration, sleep latency, sleep efficiency, sleep timing, sleep consistency, nightly heart rate variability, and daily steps from baseline (through product use) will be assessed, as measured by the health tracking wearable device.

As heart rate and heart rate variability are highly confoundable metrics, analysis of these metrics will be done on all data collected but limited to days without unusual conditions reported by the participants (e.g., unusual alcohol consumption, changes in medication, very high activity, illness, death of a family member or other extraordinary stress unrelated to study participation).

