83. Things in my surroundings appeared smaller or larger.

No, not more
than usually

Yes, much more
than usually

84. I felt exhausted.

No, not more
than usually

Yes, much more
than usually

CONFIDENTIAL

85. Time passed slowly in a tormenting way.

No, not more
than usually

Yes, much more
than usually

86. I experienced profound inner peace.

No, not more
than usually

Yes, much more
than usually

87. Everything around me seemed to be animated with life.

No, not more
than usually

Yes, much more
than usually

88. Everything happened so fast that I could not follow it all.

No, not more
than usually

Yes, much more
than usually

89. I had the feeling that something terrible was going to happen.

No, not more
than usually

Yes, much more
than usually

90. I was able to remember certain events with exceeding clarity.

No, not more
than usually

Yes, much more
than usually

91. I experienced an all-embracing love.

No, not more
than usually

Yes, much more
than usually

CONFIDENTIAL

92. There were sounds in the room that I feel were unlikely to have been real.

No , not more than usually		Yes , much more than usually
-----------------------------------	--	-------------------------------------

93. I heard a ticking, knocking, ringing, or rattling without being able to recognize the cause.

No , not more than usually		Yes , much more than usually
-----------------------------------	--	-------------------------------------

94. My experience had religious aspects to it.

No , not more than usually		Yes , much more than usually
-----------------------------------	--	-------------------------------------

Exhibit 14

Alcohol Use Disorders Identification Test (AUDIT)

The Alcohol Use Disorders Identification Test: Interview Version	

Read questions as written. Record answers carefully. Begin the AUDIT by saying "Now I am going to ask you some questions about your use of alcoholic beverages during this past year." Explain what is meant by "alcoholic beverages" by using local examples of beer, wine, vodka, etc. Code answers in terms of "standard drinks". Place the correct answer number in the box at the right.
	

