1. How often do you use drugs other than alcohol? (See list of drugs on back side.)	Never 	Once a month or less often 	2-4 times a month 	2-3 times a week 	4 times a week or more often 
2. Do you use more than one type of drug on the same occasion?	Never 	Once a month or less often 	2-4 times a month 	2-3 times a week 	4 times a week or more often 
3. How many times do you take drugs on a typical day when you use drugs?	0 	1-2 	3-4 	5-6 	7 or more 
4. How often are you influenced heavily by drugs?	Never 	Less often than once a month 	Every month 	Every week 	Daily or almost every day 
5. Over the past year, have you felt that your longing for drugs was so strong that you could not resist it?	Never 	Less often than once a month 	Every month 	Every week 	Daily or almost every day 
6. Has it happened, over the past year, that you have not been able to stop taking drugs once you started?	Never 	Less often than once a month 	Every month 	Every week 	Daily or almost every day 
7. How often over the past year have you taken drugs and then neglected to do something you should have done?	Never 	Less often than once a month 	Every month 	Every week 	Daily or almost every day 
8. How often over the past year have you needed to take a drug the morning after heavy drug use the day before?	Never 	Less often than once a month 	Every month 	Every week 	Daily or almost every day 

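### AUDIT and DUDIT change scores at Day 90 are diluted by past-year items that mostly cover pre-dose time, and the DUDIT can count the trial's own psilocybin dose

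*Protocol*

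**What the plan says.** Section 4.4.3 announces, for a list that includes AUDIT and DUDIT: "Mean changes from baseline to various study visit timepoints (e.g., Study Day 7) will be calculated for the following instruments". Neither form is scheduled at or near the one example timepoint given there. Section 12.5 adds that, for continuous questionnaires, "The statistical significance of the change from baseline" will be determined at p<0.05 for each measure, with 95% confidence intervals.

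Table 1 and Sections 7.1.3 and 7.1.9 place both forms at Screening and at the long-term follow-up visit, which Section 7.1.9 sets at "Approximately three months (i.e., 90 days) after Study Day 1"; Table 1 allows 7 days either side. Footnote 13 of Table 1 covers those who will have no 3-month visit: "The AUDIT and DUDIT should be completed at the Study Day 30 / End-of-Treatment visit if a participant prematurely discontinues from the trial".

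The forms are reproduced in the exhibits:

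- **Exhibit 14 (AUDIT)** prints two versions. The interview version opens by announcing "questions about your use of alcoholic beverages during this past year". In the self-report version, items 4-8 name the last year, and items 1-3 state no period.
- **Exhibit 15 (DUDIT)** asks about the past year in items 5-9. Item 5, for example, reads "Over the past year, have you felt that your longing for drugs was so strong that you could not resist it". Items 10-11 bring in the past year through their answer categories. Items 1-4 are in the present tense and state no period.
- The DUDIT drug list names psilocybin under hallucinogens. The only exemption printed is for pills prescribed by a doctor and taken as prescribed. Nowhere does the protocol tell participants or raters how to treat the study dose.

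**The concern.** A change score shows what happened after dosing only if the follow-up answer describes post-dose time. Two features of these forms work against that.

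First, a past-year item answered about three months after dosing describes mostly pre-dose behaviour, much of it already scored at Screening. A participant who stopped drinking on the dosing day must still report any pre-dose event that falls within the last year.

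Second, the DUDIT lists the drug that the trial administers. A participant who counts the supervised dose scores higher for having followed the protocol. The form then cannot separate that dose from other psilocybin use after dosing, which Sections 5.1.1 and 6.7.1 restrict.

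The two effects differ in direction. Overlap pulls both scales towards no change, and counting the dose pushes only the DUDIT upwards. A null DUDIT result and a raised one would both be hard to read. The question is of interest here because Section 2.3.1 reports a survey in which accompanying drug and alcohol use was among the harms described.

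**Working it through.** The protocol gives no figure of its own on this point, so there is none to reproduce. The check is date arithmetic on a 365-day recall year.

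**Inputs**

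- d, days from dose to follow-up: 90 ± 7, so 83 to 97 (Table 1, Section 7.1.9); for early discontinuers 30 ± 5, so 25 to 35 (Table 1).
- s, days from Screening to dose: 14 to 30. The lower end is the 2-week minimum in Section 4.1; the upper end is Day -30 in Section 7.1.3.

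**Pre-dose share of a past-year item = (365 − d)/365**

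| Visit | d | Pre-dose share |
|---|---|---|
| 3-month | 83 | 282/365 = 77.3% |
| 3-month | 90 | 275/365 = 75.3% |
| 3-month | 97 | 268/365 = 73.4% |
| EoT | 25 | 340/365 = 93.2% |
| EoT | 30 | 335/365 = 91.8% |
| EoT | 35 | 330/365 = 90.4% |

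**Overlap of the Screening and 3-month recall years = (365 − s − d)/365**

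- Shortest gap, s = 14 and d = 83: 268/365 = 73.4%.
- Longest gap, s = 30 and d = 97: 238/365 = 65.2%.

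**Dilution.** If a past-year answer behaves like a time average (an assumption), a complete change of behaviour on the dosing day shows at d/365 of its true size: 83/365 = 22.7% to 97/365 = 26.6%.

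**Which items are affected.** On the DUDIT, items 5-11 (7 of 11) use a past-year frame. On the interview AUDIT the opening statement covers the whole form. On the self-report AUDIT, items 4-8 name the last year. DUDIT items 1-4 and self-report AUDIT items 1-3 carry no period and can respond to recent change.

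**Study dose on the DUDIT.** Exhibit 15 prints no item codes, so assume columns score 0 to 4 from left to right. Take a participant with no other drug use who counts the dose:

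- item 1 (frequency of use): 0 to 1;
- item 3 (times taken on a typical day of use): 0 to 1;
- item 4 (how often heavily influenced): 0 to 1.

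The maximum is 1 + 1 + 1 = 3 points. The minimum is 0, for a participant who does not count the dose or who already scores at least 1 on these items. The shift in the group mean is the proportion counting the dose times the points added. For illustration, if half of 24 participants with no other drug use counted it on all three items, the mean would rise by 12/24 × 3 = 1.5 points.

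**The case against.** The strongest counter-argument is that the dose can enter only through DUDIT items 1, 3 and 4, which are in the present tense. Someone who took one supervised dose three months earlier can reasonably answer *Never* to how often they use drugs. This stands: contamination is possible, not certain. A reader might infer that every drug-naive participant gains 2 or 3 points. The form does not establish that, and zero belongs in the range. The remaining problem is that the form leaves the answer to each participant's own reading.

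Next, the forms do not look back a year throughout. Exhibit 14 holds two AUDIT versions and the protocol does not say which is used. It is therefore tempting, but wrong, to conclude that neither total can fall. Items without a stated period can fall, and 27-35% of the Screening year has left the recall window by the 3-month visit (100% minus the 65-73% overlap).

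Third, post-dose substance use is tracked elsewhere. Section 8.4 collects alcohol and recreational drug use up to the 3-month visit, and urine drug and alcohol tests are scheduled at Screening, Day 1, EoT and the 3-month visit (Table 1). A reader might infer that the trial cannot detect such use; these sources refute that. They do not, however, correct the AUDIT and DUDIT change scores.

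Finally, the endpoints are exploratory, the trial treats up to 24 participants, and the SAP may choose descriptive or item-level reporting. That limits the consequences. But the SAP cannot recover answers that were collected over the wrong period or without an instruction about the study dose.

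**Conclusion.** The point holds as a cheap improvement to two exploratory endpoints. No eligibility rule, stopping rule, primary endpoint or secondary endpoint uses these scores.

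On past-year items, about 73-77% of the recall year is pre-dose at the 3-month visit and about 92% at a Day 30 EoT visit. Early discontinuers' change scores therefore also mean something different from completers'. The overlap of 65-73% assumes Screening 14-30 days before dosing. The reduction to roughly a quarter of the true size assumes time-average answering, and applies to the past-year items, not to the whole of either score.

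On the DUDIT, the study dose adds 0 to 3 points per participant under the assumed 0-4 coding. Its size in the trial cannot be predicted, because it depends on how participants read items 1, 3 and 4. That uncertainty makes an observed rise uninterpretable. AUDIT is not affected by this second problem.

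**What to change.** 1. On the DUDIT used at EoT and the 3-month visit, state that the supervised Study Day 1 dose is not to be counted.
2. Record the frequency and quantity items (AUDIT 1-3, DUDIT 1-4) for the past 3 months at Screening and since Study Day 1 at EoT and the 3-month visit. In Section 4.4.3, define change from baseline for these two scales on those items only. At the 3-month visit the two periods are of similar length. At an EoT visit the follow-up period is only about 30 days, so those values should be identified as such.
3. Report the past-year totals descriptively, with no change-from-baseline test under Section 12.5.
4. Say which AUDIT version in Exhibit 14 is used.

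The cost is one instruction line, a few repeated items at Screening and follow-up, and edits to Section 4.4.3 and the visit lists. The downside is small: the change measure is no longer the published total score. Rewriting the recall period of both whole instruments is not needed.
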